Statistical Analysis Plan (SAP): Community-based Assessment of Skin Care, Allergies, and Eczema (CASCADE)

i. Administrative information

i.1. Version Information

Trial full title	Community-based Assessment of Skin Care, Allergies, and Eczema (CASCADE)
Trial short title	CASCADE
NIAMS grant number	R01 AR071057
Unique protocol id	00106351 (University of Utah IRB)
ClinicalTrials.gov registration	NCT03409367
SAP version	3.0
SAP version date	April 18, 2023
Senior trial statistician	[name]
Trial statisticians	[name] [name], MS
SAP associated with protocol version	13 (06Jun2021)
Trial principal investigator	[name]

i.2. Revision History

Version 1.1

Justification: Edit plan submitted with funding proposal

Timing: Before analysis, study in progress

Revisions

- Reorganization of text for clarity
- Greater detail provided of variable definitions
- Secondary analysis of ceramide-containing emollients added in response to emerging efficacy evidence

Version 2.0

Justification: Recommendation of DSMB

Timing: Before analysis, study in progress, enrollment complete

Revisions

- Eliminate interim analysis. Revise sample size calculation without alpha spending.
- Add secondary outcome of skin infections (previously appeared in table but not text)
- Add exploratory analyses of bathing and caesarean births as effect modifiers
- Add sensitivity analyses of COVID-19 pandemic effects of potentially changing prevalence of (a) primary outcome and (b) respiratory syncytial virus (RSV) over time.

Version 3.0

Justification: Clarifications in response to questions raised during chart reviews

Timing: Before analysis, study in progress, enrollment complete (April 2023)

Revisions

1. Remove secondary outcome of AD diagnosis by any method (chart, parent report, instruments). Instead, analyze competing definitions using multivariate methods.
2. Add secondary endpoint of cumulative incidence of AD at 18 months. During chart audits (ongoing), research staff have noted that many children have visits in this window who may be missing a visit in the 24-month window.
3. For skin infection secondary endpoints, separate documented physician diagnosis from topical antibiotic prescription.
4. Add pooled logistic regression as an analytic approach for time to diagnosis.

i.3. Signatures

SAP author

[name]

Senior statistician

[name]

Principal Investigator

[name]

ii. List of Abbreviations

AD	Atopic Dermatitis
AE	Adverse Event/Adverse Experience

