5.7. Analysis of Effect of Reported Emollient Use

Because the intervention uses an accessible, non-prescription topical emollient, either study arm might have users and non-users (compliant/non-compliant with study assignment). In the spirit of a *per-protocol analysis*, similar to the main analysis, we will classify participants by their reported emollient use (>weekly, on average, for the time up to diagnosis or end of follow-up) rather than assigned intervention arm. Under this coding, some participants assigned to the treatment arm might be non-users, and others assigned to the control arm may report regular emollient use; those individuals would be in different groups than under the main analysis, which uses assigned treatment arm.

Parent-reported frequency of emollient use (in days per week) will be summarized for the intervention and control arms for each quarterly follow-up time point from age 3 to 24 months (8 quarters). In this analysis, we will exclude observations after a diagnosis of AD, because emollient use is likely to reflect treatment rather than prevention. For example, if a parent reports a diagnosis of AD on the 9-month contact, that child's emollient use at 3 and 6 months will be included, but not 9 months or later. All of the definitions of AD diagnosis will be considered, i.e. GS-AD, PR-AD, CEQ-AD, etc. For missing responses, we will carry the last observation forward. Distributions over time will be graphed.

The relationship between frequency of emollient use and AD will be tested using a variable that is the average of each individual's frequency responses. We hypothesize that the intervention will increase the frequency of emollient use, and that more frequent emollient use will be associated with lower incidence of AD. If this is true, we expect that frequency will be associated with study arm (using a two-sample t-test or Wilcoxon rank-sum test, if skewed), that study arm will be associated with prevalence of AD (primary analysis), that higher frequency of emollient use will be associated with lower prevalence of AD (Equation 1 with emollient frequency substituted for study arm), and that including both treatment arm and emollient frequency in a model with AD as the outcome will change the estimate of treatment effect, which will be taken as evidence that frequency of emollient use is in the causal pathway.

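### SAP 5.7 averages emollient use up to diagnosis in cases but to 24 months in non-cases, so an age trend in use biases the use–AD estimate (toward harm if use falls)

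*SAP*

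**What the plan says.** SAP 5.7 replaces assigned arm with reported emollient use in three linked analyses.

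- **Classification in the spirit of per-protocol.** Children are grouped as users or non-users by average use "for the time up to diagnosis or end of follow-up".
- **Dose–response.** The test is run "using a variable that is the average of each individual's frequency responses", entered as "Equation 1 with emollient frequency substituted for study arm".
- **Mediation.** Arm and mean use are put in one model, and a change in the arm estimate is read as showing that use lies on the causal pathway.

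The exposure window is explicit: "we will exclude observations after a diagnosis of AD, because emollient use is likely to reflect treatment rather than prevention". For a child whose AD is reported at the 9-month contact, "that child's emollient use at 3 and 6 months will be included, but not 9 months or later". A child never diagnosed contributes up to eight contacts, from 3 to 24 months. On gaps the section says: "For missing responses, we will carry the last observation forward".

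Equation 1 (SAP 5.3) contains arm, family history and a random clinic intercept, with nothing for age or length of follow-up. SAP Table 4 applies the same pre-diagnosis window to its frequent-user variable.

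The SAP does not say how a child with AD reported by the first contact gets an average, or whether carry-forward also fills quarters removed after diagnosis. Neither document says how use changes with age.

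**The concern.** Dropping responses from diagnosis onward is right, because later use may be treatment. The difficulty is collapsing windows of unequal length and age into one mean per child. A case at 9 months is described by use at 3 and 6 months; a non-case is described by use across two years. If families apply emollient less as the child grows, cases have higher averages for arithmetic reasons alone, and nothing in Equation 1 corrects this.

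At stake is the reading of every section 5.7 result. The dose–response slope can be pushed toward harm, a real benefit can be hidden, and the mediation rule can be triggered by the construction of the variable.

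**Working it through.** **1. Inputs from the documents.** Risks are 24% and 16.8% (SAP 2.3), midpoint 20.4%; there are 1,250 children, 1:1, and eight contacts. Section 5.7 states no figure of its own. As a check on the inputs, the SAP's sample size reproduces: [1.960·√(2 × 0.204 × 0.796) + 0.842·√(0.24 × 0.76 + 0.168 × 0.832)]² / 0.072² ≈ 490.5, i.e. 491 per arm, 982 in total.

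**2. Assumptions not in the documents.** Starting use is 6 days/week (intervention) and 2–3 (control), between-child SD 1.2–2.0, within-child SD 0.8. Use changes linearly by D days/week from 3 to 24 months, and onset is either uniform over the eight quarters or front-loaded.

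**3. Gap created by the windows alone.** Use at contact k is s − D(k−1)/7.
- Non-case mean: s − D/2.
- Case reported at contact j: mean of contacts 1 to j−1 = s − D(j−2)/14.
- For the SAP's 9-month example (j = 3) the gap is D/2 − D/14 = 3D/7. With s = 6 and D = 2, that is 5.86 against 5.00.
- With uniform onset, j averages 5 over contacts 2 to 8, so the gap is D/2 − 3D/14 = 2D/7, or 0.29, 0.57 and 0.86 days/week for D = 1, 2, 3. Simulation gives 0.26, 0.51 and 0.75.

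**4. Translating the gap to an RR.** Approximately, log RR per day/week = (1 − p) × gap / variance of mean use. For arms at 6 and 3 with SD 1.2, the variance is 1.5² + 1.2² + 0.8²/8 = 3.77. With D = 2: 0.796 × 0.57 / 3.77 = 0.12, so RR ≈ 1.13.

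**5. Simulation, no true effect** (N = 1,250, 400 replicates, arms at 6 and 3, SD 1.2, modified Poisson with family history, clinic omitted). RR per day/week, with the share of replicates significant for harm (nominal 2.5%):

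| Fall | Uniform onset | Front-loaded onset |
|---|---|---|
| 0 | 1.00 (2%) | 1.00 (4%) |
| 0.5 | 1.03 (14%) | 1.04 (23%) |
| 1 | 1.07 (46%) | 1.08 (64%) |
| 2 | 1.13 (96%) | 1.17 (99%) |
| 3 | 1.20 (100%) | 1.26 (100%) |

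If use instead rises by 1 or 2, front-loaded onset gives 0.92 and 0.85.

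**6. Sensitivity to spread.** Step 4 shows why the variance of use matters. Over arms starting at 6 and 2–3 with SD 1.2–2.0 and uniform onset, falls of 1, 2 and 3 give about 1.03–1.07, 1.07–1.15 and 1.1–1.2. If all children start near 6 days/week with SD 1.2, the figures are about 1.2, 1.4 and 1.6. In that single-population case a fall of 2 gives 1.89 at SD 0.8 and 1.15 at SD 2.0.

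**7. True benefit of 0.89 per day/week.** Flat use returns 0.89. A fall of 1 gives 0.95–0.97, and power drops from 91% to 18% in the front-loaded runs. A fall of 2 gives 1.04; a fall of 3 gives 1.13, significant for harm in 96% of replicates.

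**8. Mediation model, true arm RR 1.0.** With mean use added, the arm RR becomes about 0.6–0.8 (fall of 1) or 0.4–0.65 (fall of 2). Those ranges run from arms at 6 and 3 with SD 1.2 to arms at 6 and 2 with SD 2.0; other pairings can fall outside them.

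**9. No exposure value.** With uniform onset, one eighth of cases are diagnosed by the first contact: 0.24/8 = 3.0% (0.204/8 = 2.6%).

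**10. Carry-forward.** With a fall of 2, the RR with and without it is 1.160 and 1.165 (20% intermittent gaps), 1.136 and 1.128 (5% dropout per quarter), 1.091 and 1.075 (15%).

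**11. Person-quarter alternative.** Use at the previous contact with age-quarter terms, follow-up ending at diagnosis, gives RR 0.998–1.003 under the null in every scenario. With a true 0.89 it gives 0.887–0.890 and 92–94% power.

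**The case against.** Four points can fairly be made for the plan.

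- **No decline is documented.** This stands. Flat use produces no bias and rising use reverses it. Section 5.7 will graph use over time, so a trend would be seen, but seeing it does not correct the model.
- **The sizes rest on assumed use patterns.** This also stands. Control-arm use and between-child spread largely set the slope, so only ranges with stated assumptions are defensible.
- **Harm would not always appear.** A reader might infer that any fall in use makes emollient look harmful. That holds only if emollient has no effect. Against a true 0.89, a one-day fall leaves the estimate below 1, and in these scenarios the sign reverses at a fall of about 2.
- **Carry-forward is not the cause.** A reader might blame it because it is the more familiar weakness, but step 10 shows nearly the same bias without it. Take a child whose use falls from 6 to 3 and who stops responding after 6 months. Carry-forward gives (6 + 7 × 5.571)/8 = 5.63 against a true 4.5, while averaging only the observed responses gives (6 + 5.571)/2 = 5.79, which is further off.

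None of this removes the defect: the window still depends on the outcome, and Equation 1 has no term to absorb it.

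**Conclusion.** The point holds for the non-randomised analyses in section 5.7. Falling use biases the use–AD estimate toward harm and can mask or reverse a true benefit; rising use biases it toward benefit. The mechanism follows from the SAP text, while the size is illustrative. Assuming no true effect, two arms starting at 6 and 2–3 days/week and uniform onset, the spurious RR per day/week is about 1.03–1.07, 1.07–1.15 and 1.1–1.2 for falls of 1, 2 and 3 days/week. The mediation rule is the most exposed, since with falling use it would report a pathway when neither arm nor use has any effect.

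A reader might infer that the trial's main conclusion is at risk. The documents do not support that: the primary intention-to-treat comparison in SAP 5.3 uses assigned arm and is untouched. The change should be made before analysis, but it is not critical to the primary result.

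**What to change.** Replace the person-level mean throughout section 5.7, including the user/non-user classification and the mediation model, with one of the following.

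- **Person-quarter pooled logistic model.** Use at the previous contact is the exposure, with age-quarter terms, and follow-up ends at diagnosis. Section 5.4 already allows pooled logistic regression as one of two options for onset, and the revision history records it: "Add pooled logistic regression as an analytic approach for time to diagnosis".
- **Landmark analysis.** Fix an early exposure window, restrict to children free of AD at its end, and count only later AD.

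For the person-quarter model, state a rule for the first interval: either take the use reported at baseline (listed in SAP Table 4) as its exposure, or start follow-up at the 3-month contact. Baseline use precedes randomisation and so cannot reflect assignment. Do not replace carry-forward with averaging of observed responses; in the person-quarter model, missing prior-contact use can be imputed.

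The cost is SAP wording and a person-quarter dataset built from data already collected each quarter. The estimand becomes recent use (or early use, for the landmark) rather than average use, and the SAP should say so. The comparison remains non-randomised either way.

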3.3 Treatment Arms

There are two arms in the study- intervention and control. Both study arms will receive text messages and e-mail links providing general skin care educational material

throughout the study. This general skin care information includes information regarding the use of gentle cleansers, bathing safety tips and managing rash. All dyads will be reminded of their treatment arm every three months via electronic survey and e-mail. Both arms will be contacted at the same frequency. There are no evidence-based guidelines for frequency of bathing. Because bathing practices vary between families considerably, only general bathing tips will be provided to both groups.

3.3.1 *Intervention Arm*

Dyads assigned to the intervention arm will receive a study-approved emollient of their choice by mail at regular intervals throughout the study and instructed to use the emollient once-daily over the entire body. Parents may avoid the scalp, if needed. Quarterly reminders will be sent during the course of the study instructing parents on the daily use of the study emollient. In addition, the intervention group will receive general infant skin care information identical to the control group.

3.3.2 *Control Arm*

Dyads assigned to the control arm will be instructed to refrain from routine emollient use and only use emollients on an “as needed” basis if their baby develops dry skin. Like the intervention group, dyads in the control arm will also receive general infant skin care guidelines. Information in the control educational materials will include general infant skin care recommendations, such as bathing and rashes. The information in educational materials will be current standard of care for the topics included.

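### SAP 5.7 treats an unspecified change in the arm estimate, after adding emollient frequency, as evidence of a causal pathway; the change cannot support that inference

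*SAP*

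**What the plan says.** SAP 5.7 defines the exposure as "a variable that is the average of each individual's frequency responses", in days per week. To keep treatment of AD out of that average, "we will exclude observations after a diagnosis of AD", and every AD definition counts for this purpose.

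Four findings are then expected if the emollient hypothesis is true:

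1. "we expect that frequency will be associated with study arm", by t-test or rank-sum test.
2. Arm is associated with AD in the primary analysis.
3. "higher frequency of emollient use will be associated with lower prevalence of AD", from Equation 1 with frequency in place of arm.
4. "including both treatment arm and emollient frequency in a model with AD as the outcome will change the estimate of treatment effect".

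The causal inference is attached grammatically to the fourth: "which will be taken as evidence that frequency of emollient use is in the causal pathway". No size, direction, test or interval is given for the change, and the text does not say that all four must hold.

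Equation 1 (SAP 5.3) contains arm, family history of atopy and a clinic random effect, and rules out other baseline characteristics. Protocol 3.3.2 tells control parents to avoid routine emollient use and to use it as needed "if their baby develops dry skin".

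**The concern.** Arm is randomised; emollient frequency is not. It is observed after randomisation and may share causes with AD. Dry skin is the obvious one, because the control instruction ties use to it. Dropping reports after diagnosis deals with treatment of diagnosed AD, but not with dry skin before diagnosis.

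Conditioning on such a variable can move the arm coefficient whether or not emollient affects AD. With no stated direction, a shift away from the null would count as readily as the shift towards it that simple mediation of a protective effect would produce.

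The averaging window adds a second problem. It closes at diagnosis, so it is shorter in children who develop AD. If use drifts with age, the average is then related to the outcome by construction.

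At stake is the explanation given for the trial's result: a prespecified rule would license a mechanistic claim that the analysis cannot support.

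**Working it through.** **The plan's own figure.** Section 5.7 states no error rate, so the check uses the size of the primary comparison (SAP 2.3): 24% against 16.8%, two-sided 0.05, 80% power. With pooled proportion 0.204,

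n per arm = [1.960·√(2·0.204·0.796) + 0.842·√(0.24·0.76 + 0.168·0.832)]² / 0.072² = (1.117 + 0.478)² / 0.005184 ≈ 490.5, so 491.

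This reproduces the SAP's 491 per arm (982 in total).

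**Inputs from the documents.** Control risk 24%; family-history risk ratio 2, prevalence 0.50; 1:1 allocation; 491 per arm; eight quarterly reports.

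**Assumed inputs, not in the documents.** Mean use 5.5 against 2.5 days per week (varied to 5.0 against 3.5 and 6 against 1); between-child SD 1.8; where present, an unmeasured common cause with RR 1.4 per SD for AD and correlation of about 0.5 with use; where present, a fall in use of 0.2 days per week per quarter; diagnosis timing uniform over eight quarters. Children diagnosed by the 3-month contact kept one report. Emollient frequency has no effect on AD in any scenario in the table.

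**Models.** Robust Poisson, a fallback named in SAP 5.3, with clinic omitted:

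- Model 1: log p = β0 + β1·Arm + β2·FamHx
- Model 2: Model 1 + β3·Freq
- Model 3: log p = γ0 + γ1·Freq + γ2·FamHx

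Change = (arm RR in Model 2 ÷ arm RR in Model 1) − 1. The 10% mark below is a yardstick; the SAP names none. There were 2,000 simulated trials per scenario.

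| Scenario | Arm RR, Model 1 → 2 | Change >10% | All four findings |
|---|---|---|---|
| No arm effect, no common cause | 1.00 → 1.00 | 29% | 0.6% |
| No arm effect, common cause raises AD | 1.00 → 0.77 | 96% | 0% |
| No arm effect, common cause lowers AD | 1.00 → 1.31 | 96% | 2.3% |
| No arm effect, use declines | 1.00 → 0.76 | 96% | 0% |
| Arm RR 0.7 by another route, no common cause | 0.69 → 0.69 | 35% | 43% |
| Same, common cause lowers AD | 0.70 → 0.92 | 95% | 80% |
| Same, common cause raises AD | 0.70 → 0.54 | 94% | 1.8% |
| Same, use declines | 0.70 → 0.53 | 95% | 1.1% |

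In the first row the shift averages zero but some change occurs in 100% of trials. Over the other assumed means, the share above 10% runs from 3% to 58%, and the share with all four findings from 0.2% to 1.1%.

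Repeat runs under similar assumptions gave 0.76 to 0.87 for the arm RR under dry-skin confounding. The shift is weaker when dry skin drives use among controls only (about 0.84). They gave up to 4% for all four findings with no arm effect, and 41% and 79% for the fifth and sixth rows.

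**Why the fifth row is so high.** Model 3 omits arm, so frequency stands in for arm. When arm is associated with AD for any reason, the third finding tends to follow: it occurred in 45% of trials and the second in 82%. The fourth adds nothing, because some change always occurs.

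**The rule can also miss a true pathway.** When emollient works entirely through frequency but dry skin drives use in both arms, the large-sample arm RR moves only from 0.72 to 0.74.

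**A significance test alone does not repair it.** With frequency inert and no arm effect, a 0.05 test of β3 rejects in 4.8-5.7% of trials without confounding, in 79-80% with the common cause, and in 82% with declining use.

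**The case against.** The strongest defence is that the change is the last of four expected findings and that the paragraph reads most naturally as one pattern. One of the four is an arm difference in the primary analysis and another is lower AD with higher use. Under dry-skin confounding with no arm effect, both usually fail and the arm RR moves away from 1.

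This defence is largely right for that case. A reader might infer that the SAP would declare a mechanism in a trial where neither arm nor emollient does anything. If the four findings are joint, the documents do not support that: it happens in about 4% of trials or fewer. The defence does not settle the matter, because the SAP never says the findings are joint and hangs the inference on the change alone. The joint rule also fails when the arm acts by another route. Such a route is possible, since Protocol 4.5 says parents are not blinded and may disclose allocation to clinic staff. The documents do not show that it operates.

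Three further points stand. Equation 1 does adjust for family history, which SAP 2.2 says may also influence adherence, so it would be wrong to say that no confounder of use and AD is controlled. Restriction to reports before diagnosis is already planned. And this is an explanatory analysis, so the primary result is not in question.

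**Conclusion.** The inference in SAP 5.7 is not valid as written. Read alone, the criterion cannot fail. Read jointly, it is protected when the arm has no effect (about 4% or less), but it credits frequency wrongly in about 41% of trials when the arm lowers recorded AD (RR 0.7) by another route, and in about 79% with a favourable common cause. With an adverse common cause or declining use, the joint rule is triggered in only 1-2% of such trials.

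The sizes rest on assumed use by arm, confounder strength, decline in use and diagnosis timing; the documents give none of these, and the direction of the shift depends on the sign of the common cause. The structural points do not depend on them: there is no criterion for the change, no adjustment for dry skin or prior use, and the exposure window closes at diagnosis. The consequence is confined to the mechanistic claim.

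**What to change.** Simplest: delete the sentence that reads a change in estimate as evidence of a causal pathway, and report the models with and without frequency descriptively.

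If a mechanistic claim is wanted, replace the sentence with a specified mediation analysis:

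- an estimated indirect effect with its confidence interval;
- adjustment for baseline dry skin and prior emollient use (both baseline variables in SAP Table 4) as well as family history;
- a frequency window that does not depend on when AD is diagnosed, for example use up to a fixed age, with AD counted after that age;
- a sensitivity analysis for unmeasured common causes of use and AD.

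If the four-finding pattern is kept in any form, state whether all four are required and in which direction the arm estimate must move.

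The first option costs one sentence of SAP text. The second needs some added programming but no new data. Either should be dated before arm labels are revealed.
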